2.1 Injection area

Insulin degludec should be injected subcutaneously into the thigh, or upper arm (deltoid area).

Faster-acting insulin aspart and NovoRapid® should be injected subcutaneously into the abdominal wall.

Rotation of injection sites within a given region is recommended.

2.2 Time of injection

Insulin degludec should be administered once daily at any time of the day, preferably at the same time every day.

Meal time faster-acting insulin aspart or NovoRapid® should be given 0-2 minutes before meals.

Post-meal dosing is defined as injecting 20 minutes after the start of the meal.

Main meals are defined as breakfast, lunch and main evening meal. Extra bolus dosing is allowed at the Investigator's recommendation.

3 Initiation and titration of insulin degludec, faster-acting insulin aspart and NovoRapid®

3.1 Initiation of insulin degludec

When changing basal insulin to insulin degludec, dose reduction of basal and bolus insulin needs to be considered on an individual basis in order to minimise the risk of hypoglycaemia.

At the beginning of run-in (Visit 2), the Investigator should aim at adjusting the basal-bolus ratio to be between 50:50 to 30:70. The desired total daily bolus and basal doses can be found in [Table 3-1](#). When Subjects switch from their previous insulin regimen to the trial insulin regimen at Visit 2, the total daily dosage should be calculated, and the dose of insulin degludec will be estimated according to [Table 3-1](#). e.g. if the total daily insulin dose is 28U, the Subject should receive a total of 8U of insulin degludec at the ratio of 30:70, or a total of 14U of insulin degludec at the ratio of 50:50.

Table 3-1 Start doses of total basal and bolus insulin

Total daily insulin dose (U)	Basal: bolus ratio 50:50		Basal: bolus ratio 30:70		Total daily insulin dose (U)	Basal: bolus ratio 50:50		Basal: bolus ratio 30:70	
	Total Basal (U)	Total Bolus (U)	Total Basal (U)	Total Bolus (U)		Total Basal (U)	Total Bolus (U)	Total Basal (U)	Total Bolus (U)
4	2	2	1	3	46	23	23	14	32
6	3	3	2	4	48	24	24	14	34
8	4	4	2	6	50	25	25	15	35
10	5	5	3	7	52	26	26	16	36
12	6	6	4	8	54	27	27	16	38
14	7	7	4	10	56	28	28	17	39
16	8	8	5	11	58	29	29	17	41
18	9	9	5	13	60	30	30	18	42
20	10	10	6	14	62	31	31	19	43
22	11	11	7	15	64	32	32	19	45
24	12	12	7	17	66	33	33	20	46
26	13	13	8	18	68	34	34	20	48
28	14	14	8	20	70	35	35	21	49
30	15	15	9	21	72	36	36	22	50
32	16	16	10	22	74	37	37	22	52
34	17	17	10	24	76	38	38	23	53
36	18	18	11	25	78	39	39	23	55
38	19	19	11	27	80	40	40	24	56
40	20	20	12	28	82	41	41	25	57
42	21	21	13	29	84	42	42	25	59
44	22	22	13	31	86	43	43	26	60

3.2 Titration of insulin degludec during run-in

The dose of insulin degludec will be adjusted weekly by the Investigator in the run-in period in connection with the scheduled visit/phone contacts.

Insulin degludec should be titrated based on the lowest of three pre-breakfast SMPG values measured on the three days prior to the contact in accordance with [Table 3-2](#). The fasting SMPG will be targeted at 4.0 – 8.0 mmol/L (71 – 145 mg/dL).

Table 3-2 Titration of insulin degludec

Current dose		≤ 15U	>15U
Lowest of three pre-breakfast SMPGs		Adjustment	
mmol/L	mg/dL		
≤ 3.9	≤ 70	-1	-2
4.0 – 8.0	71 - 145	0	0
8.1 – 10.0	146 - 180	+1	+2
10.1 – 15.0	181 – 270	+2	+4
> 15.1	> 270	+3	+6

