5.3.1 Basal insulin titration

At Visit 2 Subjects will be switched from their previous basal insulin analogue or Neutral Protamine Hagedorn (NPH) insulin to insulin degludec, as described in the titration guideline ([Appendix A](#)). Insulin degludec should be administered once daily at any time of the day, preferably at the same time every day. During the 12-week run-in period the basal insulin will be titrated by the Investigator on a weekly basis to the pre-breakfast glycaemic target of 4.0 - 8.0 mmol/L (71 - 145 mg/dL) in accordance with the titration guideline ([Appendix A](#)). Further adjustments of the insulin degludec dose during the treatment period should be done at the discretion of the Investigator, if needed.

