5.3.2 Bolus insulin titration

At Visit 2 Subjects will be switched from their pre-trial bolus insulin to meal-time NovoRapid®, as described in the titration guideline, see [Appendix A](#). All Subjects should have additional diabetes training including training in carbohydrate counting as described in section [8.7.2](#). NovoRapid® will not be adjusted during the run-in period unless the Investigator finds it necessary to adjust the bolus insulin for safety reasons.

At randomisation (Visit 14) Subjects will be randomised to receive meal-time faster-acting insulin aspart, or post-meal faster-acting insulin aspart or to continue using meal-time NovoRapid®.

According to the discretion of the Investigator the Subjects will be instructed to titrate the bolus insulin doses using the principles of flexible bolus dosing based on the meal carbohydrate content or to use the pre-defined bolus dosing algorithms during the treatment period, see [Appendix A](#). It is recommended that the Subjects use the method that they are most familiar with throughout the trial. The Subjects should continue using the dosing method that they use when they enter the trial, however if switching dosing method is to the benefit of the Subjects, as judged by the Investigator, the Subjects may change dosing method during the trial. In the treatment period the bolus insulin will be titrated to the pre-meal target of 4.0 – 8.0 mmol/L (71 – 145 mg/dL), and the bed-time target of 6.7 – 10 mmol/L (120 – 180 mg/dL) in a treat-to-target fashion.

Throughout the trial the bolus insulin (faster-acting insulin aspart or NovoRapid®) will be administered for each three main meals i.e. breakfast, lunch and main evening meal. Additional bolus dosing is allowed at the discretion of the Investigator.

Timing of dosing should be according to randomisation and should be as described:

- Meal-time dosing is defined as injecting 0 - 2 minutes before the meal.
- Post-meal dosing, is defined as injecting 20 minutes after the start of the meal

Timing of bolus insulin injection should be part of the “training in trial products and pen handling” and should be reinforced at each contact.

Details regarding titration of bolus insulin (pre-defined dosing algorithm and principles of flexible bolus dosing) are described in the titration guideline, see [Appendix A](#).

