6.2 Inclusion criteria

For an eligible Subject, all inclusion criteria must be answered "yes".

1. Informed consent and child assent, as age-appropriate, obtained before any trial-related activities. Trial-related activities are any procedures that are carried out as part of the trial, including activities to determine suitability for the trial. Legally Acceptable Representative (LAR) of the Subject must sign and date the Informed Consent Form (according to local requirements). The child must sign and date the Child Assent Form or provide oral assent, if required according to local requirements
2. Male or female, $1 \leq \text{age} < 18$ years at the time of signing informed consent and < 18 years at the time of randomisation
3. Diagnosed with type 1 diabetes mellitus (based on clinical judgement and supported by laboratory analysis as per local guidelines)
4. Ongoing daily treatment with a basal-bolus insulin regimen using a basal insulin analogue or NPH insulin for at least 90 days prior to the screening visit
5. Ability and willingness to take at least 3 daily meal-time related bolus insulin injections throughout the trial (Subject and LAR(s) should be evaluated as a unit)
6. Total daily dose of insulin ≤ 2.0 U/kg prior to the screening visit
7. $\text{HbA}_{1c} \leq 9.5\%$ (80 mmol/mol) analysed by the central laboratory at the screening visit

8. Ability and willingness to adhere to the protocol, including performing self-measured plasma glucose profiles (Subject and LAR(s) should be evaluated as a unit)
9. Willingness to NOT use real time CGM during the trial

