8.5.4 Insulin dose

During the trial, starting at the run-in visit (Visit 2), the Subject should be instructed to record the date and doses (units) of the breakfast, lunch, and main evening meal bolus insulin on the three days prior to a site visit/phone contact in the diary. In addition, for extra insulin boluses, date, actual clock time, dose (units), time of the previous meal, and reason for the extra bolus should be recorded.

The Subjects should also be instructed to report the date and the dose (units) of the basal insulin in the diary on the three days prior to the scheduled site visits/phone contact.

The recommended insulin doses will be individually calculated in the eCRF based on the SMPG values and the doses taken in accordance with the titration guideline, described in [Appendix A](#). If the Subject is using the principles of flexible bolus dosing based on the carbohydrate content of the meal to adjust the bolus dose, only the basal insulin dose will be calculated in the eCRF as described in [Appendix A](#).

Doses of trial products must be recorded in the eCRF.

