It is recognised that treatments differ between different regions and countries. Likewise, specific titration guidelines may not be applicable in certain clinical situations. It is important that other information, such as symptoms of hypo/hyperglycaemia, previous response to dose adjustments, other glucose measurements and other indicators of the Subject's level of glycaemic control, is taken into consideration when decisions on dosing are made. The Investigator should always use his clinical judgement to avoid safety hazards. The Investigator is responsible for the treatment of the Subjects and can therefore overrule the guideline.

To optimise and maintain glycaemic control, the Investigator should, throughout the trial be at least in weekly contact with the Subjects and/or the Subjects' legally acceptable representative(s) (LAR(s)) to assist the Subjects in adjusting insulin doses and to ensure the Subject's welfare.

2 Treatment regimens

All Subjects will be treated with insulin degludec once daily (OD) and NovoRapid® / faster-acting insulin aspart in a basal-bolus regimen in connection with meal.

At the run-in (Visit 2), eligible Subjects will be transferred from their previous basal insulin to insulin degludec OD (section [3.1](#)). During the following 12 weeks the basal insulin will be titrated by the Investigator on a weekly basis to the pre-breakfast glycaemic target (section [3.2](#)). In addition, the Subjects will be transferred to NovoRapid® as bolus insulin at the run-in (Visit 2). NovoRapid® will not be titrated during the run-in period unless the Investigator finds it necessary for safety reasons.

At randomisation (Visit 14), Subjects will be randomised to continue using meal time NovoRapid® or to receive meal time/post-meal faster-acting insulin aspart.

In the 26-week treatment period, the Investigator should focus on optimising bolus insulin on a weekly basis to the pre-meal targets. Adjustment of basal insulin dose should be minimized during the treatment phase. However, if necessary, basal insulin dose may be adjusted at the Investigator's discretion. (section [3.4](#)).

No maximum or minimum insulin dose is specified.

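### At the smallest start doses, the fixed 1 U down-steps in Appendix A can calculate a degludec or main-meal bolus dose of 0 U or less, and no floor is stated

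*Protocol*

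**What the plan says.** **Regimen.** Protocol 5.3.1 states "Insulin degludec should be administered once daily at any time of the day, preferably at the same time every day". Protocol 5.3.2 says the bolus insulin "will be administered for each three main meals i.e. breakfast, lunch and main evening meal", throughout the trial. Inclusion criterion 5 (section 6.2) asks for "Ability and willingness to take at least 3 daily meal-time related bolus insulin injections throughout the trial".

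**Start doses.** At Visit 2, under Appendix A 3.1, "the total daily dosage should be calculated, and the dose of insulin degludec will be estimated according to" Table 3-1. That table runs from 4 to 86 U/day, at basal:bolus ratios of 50:50 and 30:70.

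**Down-steps.**
- Table 3-2 (degludec, run-in): "Insulin degludec should be titrated based on the lowest of three pre-breakfast SMPG values measured on the three days prior to the contact". A value of 3.9 mmol/L or less removes 1 U at any current dose up to 15 U.
- Table 3-3 (breakfast and lunch bolus): a lowest following pre-meal value of 3.9 mmol/L or less removes 1 U from any dose below 5 U.
- Table 3-4 (evening bolus): a lowest bedtime value below the target range, which starts at 6.7 mmol/L, removes 1 U from any dose below 5 U.

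Amendment 2 corrected glucose cut-offs in Tables 3-2 and 3-4 and shows the same unit steps.

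**Floor.** Appendix A section 2 says "No maximum or minimum insulin dose is specified".

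**Who calculates.** Protocol 8.5.4: "The recommended insulin doses will be individually calculated in the eCRF based on the SMPG values and the doses taken". For flexible-dosing Subjects the eCRF calculates basal insulin only.

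**The concern.** The trial enrols from 1 year of age, and Table 3-1 itself provides for very small daily doses. At those doses 1 U can be the whole basal dose or the whole bolus for a meal. The stated rule can then recommend no basal insulin, or none for a main meal, after one low or below-target reading in three days. From a 0.5 U meal dose it gives a negative number.

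Keeping the child on the trial regimen would then require the Investigator to depart from the calculated dose, enter a reason (Appendix A 3.5) and possibly answer a central query (Appendix A 5). The discretion noted under Tables 3-3 and 3-4 is for a larger increment. Neither table mentions a smaller decrement. What is at stake is safe and uniform dosing in the youngest children, not the HbA1c comparison.

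**Working it through.** **1. Reproduce Table 3-1.** At 50:50, basal = 0.5 × total. At 30:70, basal = 0.3 × total, rounded to the nearest unit. Bolus = total − basal. The protocol's example of 28 U/day gives 0.3 × 28 = 8.4, so 8 U basal and 20 U bolus at 30:70, and 14/14 at 50:50, as printed. All 42 rows reproduce, giving 42 × 2 = 84 entries.

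**2. Basal.** With 1 U removed per weekly step, the number of down-steps to zero equals the starting dose in units.

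**3. Bolus.** A meal dose of 1 U or less goes to zero or below in one step (1.0 − 1 = 0; 0.5 − 1 = −0.5). In half units, the smallest dose above 1 U is 1.5 U. Three meals all above 1 U therefore need at least 3 × 1.5 = 4.5 U, and a total bolus of 4 U or less leaves at least one meal at 1 U or less under any split.

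All splits into three half-unit doses of at least 0.5 U:
- 2 U: 0.5/0.5/1.0
- 3 U: 0.5/0.5/2.0; 0.5/1.0/1.5; 1.0/1.0/1.0
- 4 U: 0.5/0.5/3.0; 0.5/1.0/2.5; 0.5/1.5/2.0; 1.0/1.0/2.0; 1.0/1.5/1.5
- 5 U: a split such as 1.5/1.5/2.0 avoids the problem

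**4. Results.**

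| U/day, ratio | Degludec (U) = steps to 0 | Total bolus (U) | Fewest main meals at 1 U or less |
|---|---|---|---|
| 4, 50:50 | 2 | 2 | 3 |
| 4, 30:70 | 1 | 3 | 2 |
| 6, 50:50 | 3 | 3 | 2 |
| 6, 30:70 | 2 | 4 | 1 |
| 8, 50:50 | 4 | 4 | 1 |
| 8, 30:70 | 2 | 6 | 0 |
| 10, 50:50 | 5 | 5 | 0 |
| 10, 30:70 | 3 | 7 | 0 |

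Five entries can reach 0 U or less in one step whatever the split: 4 and 6 U/day at either ratio, and 8 U/day at 50:50. Only one of them (4 U/day at 30:70) does so for degludec. Degludec 2 U (4 U/day at 50:50; 6 and 8 U/day at 30:70) needs two weekly down-steps, each triggered by a pre-breakfast value of 3.9 mmol/L or less.

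**5. When each route applies.** Table 3-2 governs run-in; later basal changes are at the Investigator's discretion. Tables 3-3 and 3-4 apply from randomisation to algorithm users only. Start bolus doses can still be in use then, because "NovoRapid® will not be titrated during the run-in period unless the Investigator finds it necessary for safety reasons".

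**The case against.** The strongest reply is that the tables produce recommendations, not administered doses. The Investigator is told to use clinical judgement and can overrule the guideline (Appendix A 1). Following the algorithm is only recommended (3.5). Contacts are weekly, and titration data are reviewed centrally within 24 hours on weekdays (Appendix A 5). The Investigator also chooses the ratio, and Subjects may change dosing method (Protocol 5.3.2). All of this stands and is why the point is minor. It does not supply a floor, and a negative calculated dose cannot be defended as a deliberate pause.

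Two further replies stand in part. The eCRF specification is not among the documents, so it may already block such doses; the point concerns the written rule. Inclusion criterion 5 is an entry test rather than a dosing rule, but sections 5.3.1 and 5.3.2 do state the regimen.

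A down-step twice the up-step is not an anomaly: at 5 U and above the steps are −2 and +1, the same ratio. A general slowing of bolus cuts is not warranted either, since 1.5 U still leaves 0.5 U after the existing step.

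Stronger readings that a reader might infer, and why they fail:
- That every entry in the 4, 6 and 8 U/day rows is exposed. This counts bolus in one step but basal in up to two. On one-step counting, 8 U/day at 30:70 drops out, because 6 U can be split 2/2/2.
- That 1 U is shown to be excessive by the Infant/Toddler correction factor in Table 5. That factor is an example for flexible dosing, whose users do not use Table 3-4.
- That children will go without insulin, or that the arms are compared unfairly. The dose remains the Investigator's decision, and the same tables apply in all arms.

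**Conclusion.** The point holds as a minor safety fix. The written rule can calculate 0 U or less in one step for 5 of 84 Table 3-1 entries, and it can take degludec 2 U to zero in two weekly run-in steps.

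The bolus count assumes that meal doses are in half units, consistent with the ½ U up-step in Tables 3-3 and 3-4 and the half-unit rounding in Appendix B 6.1. It also assumes that the whole bolus goes to the three main meals and that start doses are unchanged at randomisation. With whole-unit doses, three meals above 1 U would need 3 × 2 = 6 U, so 10 U/day at 50:50 (5 U bolus) would join the list.

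These are table entries, not children. The documents give no distribution of daily doses. The number affected is probably small: SAP section 3 refers to few Subjects below 3 years. No effect on the sample size or the primary analysis follows.

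**What to change.** State in Appendix A, and program in the eCRF, that no calculated recommendation for degludec or a main-meal bolus may be 0 U or less, and that such cases are flagged for Investigator decision. If the eCRF already does this, say so in Appendix A.

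In Tables 3-3 and 3-4, use a ½ U down-step only when the current bolus is 1 U or less: 1.0 U goes to 0.5 U, and 0.5 U is flagged. Leave the steps for larger doses unchanged. Degludec 1 U has no smaller step here and is simply flagged.

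The cost is one titration-guideline amendment and one eCRF edit check. A few recommendations become manual, and after a triggering reading a 1 U bolus falls by half instead of to zero unless the Investigator cuts further.

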3.3 Initiation of NovoRapid®

At the beginning of run-in (Visit 2), the Investigator should aim at adjusting the basal-bolus ratio to be between 50:50 to 30:70. The desired total daily bolus and basal doses can be found in [Table 3-1](#). When Subjects switch from their previous insulin regimen to the trial insulin regimen at Visit 2, the total daily insulin dosage will be calculated, and the dose of NovoRapid® will be estimated according to [Table 3-1](#) e.g. if the total daily insulin dose is 28U, the Subject should receive a total of 20U of NovoRapid® at the ratio of 30:70, or a total of 14U of NovoRapid® at the ratio of 50:50.

3.4 Titration of bolus insulin from randomisation

Titration of bolus insulin will be performed from randomisation (Visit 14) and onwards while the adjustments of basal insulin dose(s) can be performed according to the Investigators' discretion.

For the purpose of insulin titration the Subjects will be instructed to perform 4-point profiles on the three days prior to a scheduled site visit/phone contact every week during the conduct of the trial.

Faster-acting insulin aspart/NovoRapid® titration will be done once weekly based on the lowest pre-meal and bedtime SMPG measured on the three days prior to the scheduled site visit/phone contact in accordance with [Table 3-3](#) and [Table 3-4](#) respectively, or using principles of flexible bolus

dosing based on the carbohydrate content of a meal [3.4.2](#). It is recommended that the Subjects use the method that they are most familiar with.

3.4.1 Bolus dosing according to the algorithm

The pre-meal SMPG will be targeted at 4.0 – 8.0 mmol/L (71 – 145 mg/dL), while the bed-time SMPG will be targeted at 6.7–10 mmol/L (120–180 mg/dL)¹⁰.

3.4.1.1 Pre-breakfast and pre-lunch bolus insulin titration

- Pre-breakfast faster-acting insulin aspart/NovoRapid® will be adjusted according to the lowest pre-lunch SMPG value measured on the three days prior to the site visit/phone contact [Table 3-3](#)
- Pre-lunch faster-acting insulin aspart/NovoRapid® will be adjusted according to the lowest pre-main evening meal SMPG value measured on the three days prior to the site visit/phone contact [Table 3-3](#)

Table 3-3 Titration of pre-breakfast and pre-lunch faster-acting insulin aspart/NovoRapid®

Current dose		< 5U	≥ 5U
Lowest pre-meal SMPG value measured on the three days prior to the site visit/phone contact		Adjustment	
mmol/L	mg/dL		
≤ 3.9	≤ 70	-1	-2
4.0 – 8.0	71 – 145	0	0
≥ 8.1 ^a	≥ 146	+½	+1

a. It is at the Investigator's discretion to use a higher dose increment.

3.4.1.2 Pre-dinner bolus insulin titration

- Before main evening meal faster-acting insulin aspart/NovoRapid® will be adjusted according to the lowest bedtime SMPG value measured on the three days prior to the site visit/phone contact [Table 3-4](#)

Table 3-4 Titration of pre-dinner faster-acting insulin aspart/NovoRapid®

Current dose		< 5U	≥ 5U
Lowest bed-time SMPG value measured on the three days prior to the site visit/phone contact		Adjustment	
mmol/L	mg/dL		
≤ 6.7	≤ 120	-1	-2
6.7 – 10.0	120 – 180	0	0
≥ 10.0 ^a	≥ 180	+½	+1

a. It is at the Investigator's discretion to use a higher dose increment.

3.4.2 Subjects following principles of flexible bolus insulin dosing

NovoRapid® and faster-acting insulin aspart may be titrated in accordance with principles of flexible bolus dosing whereby the meal carbohydrate content and pre-prandial plasma glucose value are used to determine the bolus insulin dose. This method is applicable to Subjects and/or LAR(s) who have demonstrated prior hands-on experience with using this method of determining bolus insulin doses. At visit 2, it is the responsibility of the Investigator to ensure that the Subject and/or LAR(s) are adequately trained and comfortable using this method. If more training is needed this should be carried out according to local practise.

Using this method, bolus insulin dose adjustment is conducted several times daily in accordance with the Insulin:Carbohydrate (I:Carb) ratio and the plasma glucose correction factor (sensitivity factor). Bolus insulin dose consists of meal bolus to cover for carbohydrates consumed in the meal and, if required, a correction dose (to supplement or reduce the dose based on the difference between the SMPG and the target).

The I:Carb ratio expresses the amount of carbohydrate (in grams) for which 1U of bolus insulin would effectively minimise postprandial plasma glucose excursions. The plasma glucose correction factor (sensitivity factor) expresses the expected reduction in plasma glucose per 1U of bolus insulin. The I:Carb ratio and the correction factor (sensitivity factor) per type of meal should be recorded at Visit 2 and should, if needed, be adjusted at the discretion of the Investigator during the weekly contacts based on the reviewed SMPGs.

The target pre-prandial plasma glucose ranges are 4.0 – 8.0 mmol/L (71 – 145 mg/dL) for breakfast and lunch and 6.7 – 10.0 mmol/L (120-180 mg/dL) for bedtime.

In the following, an example on how to cover a Subject's prandial insulin dose is provided. In case of hypoglycaemic episodes, the dose will be reduced at the Investigator's discretion.

Example 1 – Carbohydrate coverage of a meal and plasma glucose correction dose:

At lunchtime, a Subject has pre-prandial plasma glucose of 10.0 mmol/L (180 mg/dL) and intends to eat a meal containing 60 g of carbohydrates. The I:Carb ratio has been estimated to 1U:10g.

The meal coverage dose is calculated as follows:

$$\text{Total carbohydrate in meal} * \text{I:Carb ratio} = 60 \text{ g} * (1\text{U}/10\text{g}) = 6\text{U}.$$

The plasma glucose correction factor (sensitivity factor) has been estimated to be 2 mmol/L (36 mg/dL) per 1U. The pre-prandial plasma glucose target range is 4.0 – 8.0 mmol/L (71 – 145 mg/dL) for breakfast and lunch. The Subject was advised to correct to the target plasma glucose of 8.0 mmol/L (145 mg/dL) at this meal.

The correction dose can be calculated as follows: (Pre-prandial plasma glucose – target plasma glucose) ÷ plasma glucose correction factor = bolus insulin unit

$$(10.0 \text{ mmol/L} - 8.0 \text{ mmol/L}) \div 2.0 \text{ mmol/L/U} = 1\text{U} \text{ or}$$

$$(180 \text{ mg/dL} - 145 \text{ mg/dL}) \div 36 \text{ mg/dL/U} = 1\text{U}$$

Thus this Subject needs 7U of bolus insulin to cover for the meal and correct for hyperglycaemia before the meal.

Examples for initial plasma glucose correction factors and I:Carb ratios according to age group are presented in [Table 5](#).

Table 5 Plasma glucose correction factors and I:Carb ratios

Age group	Plasma glucose correction Factor	I:Carb ratio
Infant/Toddler	1U:15 mmol/L (270 mg/dL)	1U:60g
Pre-Pubertal	1U:10 mmol/L (180 mg/dL)	1U:45g
Early Puberty	1U:5 mmol/L (90 mg/dL)	1U:15 g
Older Adolescent	1U:2.5 mmol/L (45 mg/dL)	1U:10g

